2.7.1 Missing data

Missing data can impact the integrity and credibility of any clinical study. Therefore, all attempts will be made to minimize missing data. These attempts include training of the investigators and site personnel and discussions with the participants during the informed consent process on the importance of accurate and complete data collection. The study sponsor will track issues with sites regarding missing data through the usual monitoring process.

2.8 Study population

The study population is comprised of adults with chronic rhinitis. To be eligible for enrollment in the study the patients must meet all the inclusion criteria and none of the exclusion criteria.

2.8.1 Inclusion criteria

Study participants MUST meet all of the following criteria:

- 1. Be \geq 21 years of age.
- 2. Has been diagnosed with chronic nonallergic or allergic rhinitis.
- 3. Have moderate to severe symptoms of rhinorrhea (individual rTNSS symptom rating of 2 or 3), mild to severe symptoms of nasal congestion (individual rTNSS symptom rating of 1, 2, or 3), and a minimum total rTNSS score of 4 (out of 12) at baseline.
- 4. Have an allergy test (by skin prick or intradermal testing or by validated *in vitro* tests for specific Immunoglobin E [IgE]) on file within 12 months of the baseline visit.
- 5. Be an appropriate candidate for bilateral ClariFix treatment performed under local anesthesia.
- 6. Be willing and able to comply with all study elements, as indicated by their written informed consent.

2.8.2 Exclusion criteria

Study participants MUST NOT meet any of the following criteria:

- 1. Have clinically significant anatomic obstructions that, in the investigator's opinion, limit access to the posterior nose, including but not limited to severe septal deviation or perforation, nasal polyps, and/or sinonasal tumor.
- 2. Have had previous sinus or nasal surgery within 6 months of study enrollment.
- 3. Have previously undergone cryotherapy or other surgical interventions for rhinitis.
- 4. Have an active nasal or sinus infection.
- 5. Have rhinitis symptoms that are primarily due to seasonal allergies.
- 6. Have plans to (or otherwise anticipates the need to) undergo an ENT procedure concurrently or within 3 months after the study procedure.
- 7. Is on prescribed anticoagulants (eg, warfarin, Plavix) or 325 mg aspirin that cannot be discontinued before the procedure (81 mg aspirin and herbal supplements are acceptable).
- 8. Be unable to discontinue ipratropium bromide (IB) at least 14 days before baseline and through the 90-day follow-up visit.
- 9. Have a history of chronic epistaxis or experienced a significant epistaxis event (defined as epistaxis event requiring medical intervention) in the past 3 months.
- 10. Have a history of rhinitis medicamentosa.
- 11. Have had previous head and/or neck irradiation.
- 12. Have an allergy or intolerance to local anesthetic agents.
- 13. Have cryoglobulinemia, paroxysmal cold hemoglobinuria, cold urticaria, Raynaud's disease, and/or open and/or infected wounds at or near the target tissue.
- 14. Have a neurological, medical, psychiatric condition, or social circumstance that would potentially increase risk, interfere with study participation, or confound interpretation of study data
- 15. Be participating in another clinical research study.

2.9 Concomitant medications

Concomitant medications that should be documented at screening and throughout the study include the following:

- Medications taken for rhinitis, allergies, asthma, sinusitis, migraines, and GERD (or any other ENT, head and neck, respiratory, and/or airway related conditions or systems), including saline.
- Medications administered to treat a study-related adverse event.

Additionally, any medication, as deemed by the investigator, to present a potential safety risk at the time of the procedure (eg, beta-blockers) should be noted as a concomitant medication.

2.9.1 Prohibited medications

Any participants taking nasal anticholinergic sprays (eg, IB) will be instructed at screening to discontinue use at least 14 days before the baseline visit and through the 90-day follow-up visit.

Participants will also be instructed not to change their baseline concomitant medications (start/stop or change of dose) before the 90-day study follow-up, unless required to treat an adverse event.

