2.2.2 Secondary objectives

- To demonstrate durability of the treatment effect through 365 days of follow-up.
- To support peer-reviewed publications on the ClariFix technology.

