2.3 Study endpoints

2.3.1 Primary endpoint

The primary endpoint is the percentage of responders at 90 days. Responders are defined as participants with a 30% or greater reduction in rTNSS relative to baseline. The active treatment group will be compared with the sham-control group.

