2.3.2 Secondary endpoints

The following secondary endpoints will compare the active treatment group with the sham-control group at 30-day and 90-day follow-ups:

- Mean change from baseline in rTNSS score
- Mean change from baseline in Standardized Rhinoconjunctivitis Quality of Life Questionnaire (RQLQ(S)) score
- Mean change from baseline in EuroQol 5-dimension survey (EQ-5D-5L) scores
- Percent of patient satisfaction at follow-up
- Rate of serious device- or procedure-related adverse events (SAEs)

The following secondary endpoints will be assessed at all follow-ups for all participants who receive active treatment (randomized or crossover):

- The percentage of responders
- The mean change from baseline in rTNSS score
- The mean change from baseline in RQLQ(S) score
- Mean change from baseline in EQ-5D-5L scores
- Percent of patient satisfaction at follow-up

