2.10 Methods and procedures

Study methods and procedures are described below. An overview of the required study assessments at each follow-up visit is provided in **Table 2**. Each participant's follow-up schedule is based on the procedure date. Control participants who elect crossover after the 90-day visit will undergo a ClariFix procedure and then continue follow-up through 365 days after the active treatment.

Table 2. Study Assessment Schedule

	Study Visit (window)							
Study evaluation	Screening (up to 30 days preprocedure) ^a	Baseline (up to 7 days preprocedure) ^b	Randomization & procedure (day 0) ^{b,c}	30-Day (± 7 days) °	90-Day (± 14 days) °	180-Day (± 21 days) ^c	270-Day (± 21 days) ^c	365-Day (± 21 days)≎
Informed consent	✓							
Demographics and medical history	✓							
Clinical evaluation	✓							
Eligibility assessment	✓	✓						
Urine pregnancy test ^d			✓					
Randomize to treatment arm			✓					
Procedure (active or sham)			✓					
Record procedure information			✓					
Blinding questionnairee			✓	✓	✓			
Adverse events			✓	✓	✓	✓	✓	✓
Concomitant medicationsf	✓	✓	✓	✓	✓	✓	✓	✓
Quantitative endoscopic rhinoscopy ^g	✓		✓	✓	✓	✓	✓	✓
rTNSS	✓	✓		✓	✓	✓	✓	✓
RQLQ(S)		✓		✓	✓	✓	✓	✓
EQ-5D-5L		✓		✓	✓	✓	✓	✓
NOSE		✓		✓	✓	✓	✓	✓
Participant satisfaction				✓	✓	✓	✓	✓

^a The procedure must take place within 30 day of the screening visit.

The participant must discontinue use of IB at least 14 days before the baseline visit. The procedure must be scheduled within 7 days of the baseline visit (it can be the same day as baseline if all criteria are met).

c Control participants electing to crossover to active treatment will undergo a ClariFix procedure and then continue follow-up through 365 days after the active treatment.

d Urine pregnancy tests are required for all women of childbearing potential before the procedure.

Blinding questionnaire is only completed for the initial randomized treatment procedure (active or control), not for crossover treatments.

	Study Visit (window)							
Study evaluation	Screening (up to 30 days preprocedure) ^a	Baseline (up to 7 days preprocedure) ^b	Randomization & procedure (day 0) ^{b,c}	30-Day (± 7 days) °	90-Day (± 14 days) °	180-Day (± 21 days)∘	270-Day (± 21 days) ^c	365-Day (± 21 days)∘

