2.10.3 Baseline visit

The following activities are conducted at the baseline visit:

- 1. Participant completes questionnaires: rTNSS, RQLQ(S), EQ-5D-5L, and Nasal Obstruction Symptom Evaluation (NOSE).
- 2. Record concomitant medications (confirm discontinuation of IB for at least 14 days prior, if applicable).
- 3. Review eligibility criteria; if participant continues to meet eligibility criteria, schedule for randomization and procedure. The study procedure must be scheduled within 7 days of the baseline visit (the procedure can occur on the same day as the baseline visit if all criteria are met).

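### The day-180 to day-365 responder rates and mean changes have no rule for rhinitis medication resumed or added after day 90, so they cannot alone support durability

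*Combined protocol and SAP*

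**What the plan says.** **Medication rules.** Section 2.9.1 requires participants on nasal anticholinergic sprays to "discontinue use at least 14 days before the baseline visit and through the 90-day follow-up visit". Exclusion criterion 8 (section 2.8.2) sets the same window for ipratropium (IB). Section 2.9.1 also instructs participants "not to change their baseline concomitant medications (start/stop or change of dose) before the 90-day study follow-up", except to treat an adverse event. Neither rule is extended past day 90.

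**Baseline.** A footnote to Table 2 states: "The participant must discontinue use of IB at least 14 days before the baseline visit". At the baseline visit (section 2.10.3) staff must "confirm discontinuation of IB for at least 14 days prior, if applicable".

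**Late endpoints.** The first secondary objective (section 2.2.2) is: "To demonstrate durability of the treatment effect through 365 days of follow-up". Section 2.3.2 states: "The following secondary endpoints will be assessed at all follow-ups for all participants who receive active treatment (randomized or crossover"; the list that follows includes the responder rate and the mean changes in rTNSS, RQLQ(S) and EQ-5D-5L. The responder rule in section 2.3.1 is: "Responders are defined as participants with a 30% or greater reduction in rTNSS relative to baseline". It carries no medication condition, and section 2.11.1 adds none.

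**Analysis rules.** For long-term follow-up, section 2.7 says only that crossover participants are analyzed together with those randomized to active treatment. Section 2.7.1 covers prevention of missing data. Section 2.3.3 defers only exploratory outcomes to a Statistical Analysis Plan.

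**Data collected.** Section 2.9 and Table 2 require rhinitis medication to be recorded at every visit through day 365.

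**The concern.** A change from baseline is easiest to read when background treatment is comparable at both ends. Here one end is measured off anticholinergics, and the other is measured when participants may use any rhinitis medication. A prior ipratropium user whose symptoms return in month 5, and who restarts the spray, can be a responder at day 180 under the rule as written. So can someone who adds a nasal steroid or an antihistamine.

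There is no comparator to absorb this. Under sections 2.4 and 2.10.9, sham participants either cross over or leave the study after the 90-day visit, so the late results come from actively treated participants only. Participants whose benefit fades have the most reason to add medication, so a loss of effect could go unseen in them. What is at stake is the durability claim.

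**Working it through.** **1. The plan's own figure.** No figure is stated for the late analyses. The one sample size, in section 2.6, is for the 90-day endpoint. With 73.5% against 45%, one-sided alpha 0.025, 90% power and pooled variance, the two-proportion formula gives 61 per arm, or 122 in total, with power 90.3%. The stated 122 is reproduced, and nothing below changes it.

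**2. The two ends of the comparison.**

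| | Baseline | Day 90 | Days 180, 270, 365 |
|---|---|---|---|
| Nasal anticholinergic | Off for at least 14 days | Off | No restriction stated |
| Other baseline medication | As taken at baseline | Not to be changed since baseline, adverse-event treatment excepted | No restriction stated |
| Concurrent sham group | Yes | Yes | No |
| Medication condition in the responder rule | n/a | None | None |

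For crossover participants the late columns are less certain. They must meet eligibility again, and their assessments restart with the new active procedure (Investigational Plan Summary; section 2.4), so the day-90 limits may restart too. The plan does not say so expressly.

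**3. How easily the threshold is crossed.** Section 2.8.1 requires a baseline rTNSS of at least 4 and a rhinorrhea item of 2 or 3. A 2-point fall is 2/4 = 50%, 2/5 = 40% or 2/6 = 33%, and each passes 30%; 2/7 = 29% does not. At a baseline of 4 to 6, improvement in the rhinorrhea item alone can therefore make a responder.

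**4. Size if medication is added.** Let r be the responder rate without new medication, q the share of non-responders who resume or add medication, and g the share of those who then cross the threshold.

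Reported rate = r + (1 − r) × q × g

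The documents give neither q nor g, and no late value of r. Assumed: q from 20% to 50%, g from 30% to 50%. For r, two values are used: 73.5%, the day-90 active rate in section 2.6, as if fully maintained; and 55%, an assumption for partial loss.

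| r | q, g | Inflation | Reported rate |
|---|---|---|---|
| 73.5% | 20%, 30% | 0.265 × 0.06 = 1.6 points | 75.1% |
| 73.5% | 50%, 50% | 0.265 × 0.25 = 6.6 points | 80.1% |
| 55% | 20%, 30% | 0.45 × 0.06 = 2.7 points | 57.7% |
| 55% | 50%, 50% | 0.45 × 0.25 = 11.3 points | 66.3% |

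A wider grid (r from 45% to 73.5%, q from 10% to 50%, g from 25% to 75%) runs from 0.265 × 0.025 = 0.7 points to 0.55 × 0.375 = 20.6 points.

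**5. Size of a composite rule.** If an observed 73.5% are responders and 10%, 20% or 30% of them are on new or resumed medication, counting those as non-responders gives 0.735 × 0.9 = 66.1%, 0.735 × 0.8 = 58.8% or 0.735 × 0.7 = 51.4%.

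**6. The other direction.** A participant who improves and cuts medication may score worse than on unchanged treatment. That lowers the as-observed rate, and nothing in the documents allows it to be sized.

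**The case against.** The strongest reply is that a long-term summary taken as observed, under whatever care participants receive, is a legitimate target, and that medication use is recorded so a reader could see it alongside. This stands as far as it goes: the as-observed rate is worth reporting. But section 2.2.2 promises durability of the treatment effect, and nothing in the plan commits to showing medication use beside the late results or to reading them in that light.

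Several stronger readings are tempting, and the documents do not support them:

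- *The late rates must be inflated.* The net direction is unknown, because reduced medication works the other way and no usage figures are given.
- *The late responder rates and mean changes are the only durability data.* Satisfaction, NOSE and endoscopic rhinoscopy are also collected at days 180, 270 and 365, although medication could influence these too.
- *Baseline was taken on stable background medication.* Section 2.9.1 sets a pre-baseline period for nasal anticholinergics only.
- *A medication rule would isolate the device effect.* Participants are unblinded at day 90 and there is no late control, so natural course, expectation and regression to the mean remain.

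A composite also needs care. Section 2.9 includes saline among the recorded medications, and section 2.10.5 allows it after the procedure. Taken literally, a rule based on that list would fail participants for using saline, or for medication given to treat an adverse event. Making a composite the sole main rate would be a debatable choice. Finally, a separate analysis plan could contain a rule; none is in the file, and the protocol defers only exploratory outcomes to it.

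**Conclusion.** The concern holds in a limited form. Followed as written, the plan yields day-180, -270 and -365 responder rates and mean changes that mix ClariFix with any rhinitis medication resumed or added after day 90, and these cannot by themselves show durability. For crossover participants this applies from whichever day-90 visit ends their restrictions.

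The possible inflation from added medication is 1.6 to 6.6 points at an underlying rate of 73.5% and 2.7 to 11.3 points at 55%. Both ranges rest on the assumed shares in the working. Reduced medication would offset some or all of it. A reader might infer that the main result is compromised. It is not: the primary endpoint, the other randomized 30- and 90-day comparisons and the sample size are unaffected.

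**What to change.** Amend sections 2.3.2 and 2.7 before the late data are analyzed:

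- Report each day-180, -270 and -365 responder rate as observed. Beside it, report a composite rate that counts as a non-responder anyone who at that visit is using a nasal anticholinergic, or a rhinitis medication started or (where dose is recorded) increased since baseline. Exclude saline and medication given to treat an adverse event.
- Give the mean changes with a matching sensitivity analysis.
- Tabulate at each visit the share of participants who increased, kept or reduced rhinitis medication.
- State that the durability conclusion rests on both rates.
- For crossover participants, state which baseline and which 90-day visit these rules refer to.

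The cost is a little more analysis and a composite late rate somewhat below the as-observed one. Medication is already recorded at these visits, but the protocol does not say that dose is, so the part of the rule on increases depends on what the case report form captures. Permitted care after day 90 and the sample size stay as they are.

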2.10 Methods and procedures

Study methods and procedures are described below. An overview of the required study assessments at each follow-up visit is provided in **Table 2**. Each participant's follow-up schedule is based on the procedure date. Control participants who elect crossover after the 90-day visit will undergo a ClariFix procedure and then continue follow-up through 365 days after the active treatment.

Table 2. Study Assessment Schedule

	Study Visit (window)							
Study evaluation	Screening (up to 30 days preprocedure) ^a	Baseline (up to 7 days preprocedure) ^b	Randomization & procedure (day 0) ^{b,c}	30-Day (± 7 days) °	90-Day (± 14 days) °	180-Day (± 21 days) ^c	270-Day (± 21 days) ^c	365-Day (± 21 days)≎
Informed consent	✓							
Demographics and medical history	✓							
Clinical evaluation	✓							
Eligibility assessment	✓	✓						
Urine pregnancy test ^d			✓					
Randomize to treatment arm			✓					
Procedure (active or sham)			✓					
Record procedure information			✓					
Blinding questionnairee			✓	✓	✓			
Adverse events			✓	✓	✓	✓	✓	✓
Concomitant medicationsf	✓	✓	✓	✓	✓	✓	✓	✓
Quantitative endoscopic rhinoscopy ^g	✓		✓	✓	✓	✓	✓	✓
rTNSS	✓	✓		✓	✓	✓	✓	✓
RQLQ(S)		✓		✓	✓	✓	✓	✓
EQ-5D-5L		✓		✓	✓	✓	✓	✓
NOSE		✓		✓	✓	✓	✓	✓
Participant satisfaction				✓	✓	✓	✓	✓

^a The procedure must take place within 30 day of the screening visit.

The participant must discontinue use of IB at least 14 days before the baseline visit. The procedure must be scheduled within 7 days of the baseline visit (it can be the same day as baseline if all criteria are met).

c Control participants electing to crossover to active treatment will undergo a ClariFix procedure and then continue follow-up through 365 days after the active treatment.

d Urine pregnancy tests are required for all women of childbearing potential before the procedure.

Blinding questionnaire is only completed for the initial randomized treatment procedure (active or control), not for crossover treatments.

	Study Visit (window)							
Study evaluation	Screening (up to 30 days preprocedure) ^a	Baseline (up to 7 days preprocedure) ^b	Randomization & procedure (day 0) ^{b,c}	30-Day (± 7 days) °	90-Day (± 14 days) °	180-Day (± 21 days)∘	270-Day (± 21 days) ^c	365-Day (± 21 days)∘

f Concomitant medications include those taken for rhinitis, allergies, asthma, sinusitis, migraines, and GERD (or any other ENT, head and neck, respiratory, and/or airway related conditions or systems), including saline; and medications taken to treat a study-related adverse event. Additionally, any medications deemed to present a potential safety risk at the time of the procedure (eg, beta-blockers) should be documented.

2.10.1 Eligibility assessment

Patients are considered eligible for this study if they meet **all** the inclusion criteria and **none** of the exclusion criteria as defined in **Section 2.8**. The principal investigator or subinvestigator at each investigational center will determine patient eligibility based on the inclusion/exclusion criteria. Participants will be considered enrolled at the time of randomization and procedure.

2.10.2 Screening visit

The initial screening visit can occur up to 30 days before the study procedure.

For individuals who have been prescreened for eligibility, the following procedures/assessments will be performed at the screening visit:

- 1. Informed consent form signed.
- 2. Participant completes the rTNSS questionnaire.
- 3. Record demographics and patient medical and surgical history (with focus on nasopharyngeal, ocular, and respiratory conditions; allergies; and rhinitis history).
- 4. Record concomitant medications (See Section 2.9).
- 5. Clinical evaluation, including visual inspection of eyes, mouth/throat, and ears to confirm participant's overall health and suitability to undergo the study procedure.
- 6. Perform a quantitative endoscopic rhinoscopy before administration of nasal decongestant to evaluate nasal congestion.
- 7. Administer nasal decongestant. If the participant is a woman of childbearing potential, use medical judgement to select a decongestant (eg, oxymetazoline) that is safe to use during pregnancy.
- 8. Repeat quantitative endoscopic rhinoscopy to evaluate nasal structures, treatment site, and assess degree/extent of rhinorrhea and postdecongestant nasal congestion.

Quantitative endoscopic rhinoscopy will consist of an assessment of nasal congestion before administration of decongestant and an assessment to include rhinorrhea and nasal congestion after administration of a decongestant.

- 9. Determine if an allergy test conducted within 12 months is available and whether participant's rhinitis is allergic or nonallergic. If an allergy test is not on file, a blood allergy test (IgE level) should be scheduled to take place before the baseline visit.
- 10. Review of study eligibility criteria.

Patients not meeting the screening criteria will be considered screen failures and are not eligible for participation in the study.

Participants continuing in the study will be scheduled for the baseline visit. For participants using IB, they must discontinue IB usage at least 14 days before the baseline visit.

2.10.3 Baseline visit

The following activities are conducted at the baseline visit:

- 1. Participant completes questionnaires: rTNSS, RQLQ(S), EQ-5D-5L, and Nasal Obstruction Symptom Evaluation (NOSE).
- 2. Record concomitant medications (confirm discontinuation of IB for at least 14 days prior, if applicable).
- 3. Review eligibility criteria; if participant continues to meet eligibility criteria, schedule for randomization and procedure. The study procedure must be scheduled within 7 days of the baseline visit (the procedure can occur on the same day as the baseline visit if all criteria are met).

2.10.4 Randomization and blinding

Randomization assignments will be generated by in independent statistician using variable block size distribution by site with a 1:1 allocation to active or sham treatment. Randomization will also be stratified by allergy subgroup (allergic, nonallergic). The randomization schedule will be entered into the Medrio electronic data collection (EDC) randomization module. Randomization will occur on the day of the procedure and after all baseline data have been collected and eligibility has been confirmed. All randomized and treated participants will be considered enrolled. Confirmation of randomization assignment from EDC will be printed and filed in the study record.

This is a single-blind study; participants will be blinded to the randomized assignment. To facilitate blinding, control participants will undergo a sham procedure using the ClariFix device without a cryogen cannister. To support blinding, participants will wear blindfolds during the procedure to limit any visual clues that may suggest the treatment assignment. A separate device with a canister held near the participant will be used to provide the sound of the gas release from the cannister. A standardized script for the physician/staff will be used during the procedure to assure blinding. Additionally, local anesthesia regimes will be the same for both treatment groups within each investigational center.

Participants will complete a blinding questionnaire at completion of the procedure and at the 30-day and 90-day follow-up visits to assess the adequacy of the blinding procedures. Upon

completion of their 90-day visit, each participant will be unblinded. Sham control participants will be offered the opportunity to receive active treatment if they wish and still meet eligibility criteria.

Before the 90-day visit, unblinding of participants will only occur when medically necessary. In the event of a device-or procedure-related SAE, the sponsor may authorize the site to unblind the participant in order to adequately assess the event.

